8.6.1.2 Deaths

All deaths reported during the study will be tabulated and summarized by treatment arm.

8.6.2 Other Serious Adverse Events

Serious adverse events will be tabulated and summarized by MedDRA Preferred Term and treatment arm.

8.6.3 Clinical Laboratory Evaluations

Clinical laboratory results will be collected at Screening, Day 1, and at the Safety Follow-up Visit. All laboratory results will be classified according to the NCI CTCAE version 4.03, and will be summarized by worst grade per patient and treatment arm.

9 ADMINISTRATIVE PROCEDURES AND STUDY MANAGEMENT

9.1 Investigator Responsibilities

9.1.1 Good Clinical Practice

It is the responsibility of the Principal Investigator to oversee the safety of the patients at their site. The Investigator will ensure that this study is conducted in full compliance with the principles of the “Declaration of Helsinki” (as amended in Tokyo, Venice, Hong Kong, and South Africa), ICH guidelines, or with the laws and regulations of the country in which the research is conducted. By signing the US Form FDA 1572, “Statement of Investigator”, the Investigator commits to adhere to applicable sections of the US CFR parts 50 “Protection of Human Patients”, 54 “Financial Disclosure by Clinical Investigators”, 56 “Institutional Review Boards”, and 312 subpart D “Responsibilities of Sponsors and Investigators”. All Investigators will ensure adherence to ICH guidelines for GCP and Clinical Safety Data Management.

9.1.2 Institutional Review Board/Ethics Committee Approval

The Investigator shall assure that the IRB/EC will provide initial and continuing review of the study. Prior to screening and enrollment of study patients, documented IRB/EC approval of the protocol, ICF and any patient materials must be obtained and provided to Spectrum or its designee.

9.1.3 Informed Consent

The investigator will ensure that the method of obtaining and documenting the Informed Consent complies with ICH-GCP and all applicable regulatory requirement(s). Informed Consent must be obtained before study procedures are performed, unless performed as standard of care. The subject's source documents shall document the informed consent process and that Informed Consent was obtained prior to study participation. A copy of each signed ICF must be provided to the patient or the patient's legally authorized representative. All signed ICFs must remain in each patient's study file and must be available for verification at any time.

9.1.4 Study Files and Retention of Records

The Investigator will retain all study records until at least 2 years after the last approval of a marketing application or at least 2 years have elapsed since the formal discontinuation of clinical development of the investigational product. These documents will be retained for a longer period, however, if required by the applicable regulatory requirements or by an agreement with Spectrum. If the Investigator relocates, or for any reason desires to dispose of the records, the study records may be transferred to another institution, another investigator, or to Spectrum upon written agreement between the Investigator and Spectrum.

9.2 Recording and Collecting of Data

In accordance with ICH and GCP guidelines, the Investigator will maintain complete, accurate, legible, and easily retrievable data, and will allow personnel authorized by Spectrum access to all study data at any time. Such data shall also be secured in order to prevent loss of data.

9.2.1 Case Report Forms

At scheduled monitoring visits, CRFs will be verified against source documentation and submitted as final data. Any subsequent changes to the CRFs are to be performed in accordance with Spectrum's standard operating procedures for editing and clarifying CRFs. Data entry will be performed by the sites using an electronic data capture (EDC) system.

9.2.2 Drug Accountability

In accordance with all applicable regulatory requirements, the Investigator or designated site staff is to maintain study treatment accountability records throughout the course of the study. This person(s) will document the amount of Qapzola administered to patients. The CRA will review inventory and accountability documentation during monitoring visits.

The Investigator will not supply investigational study drugs to other investigators not listed on the US Form FDA 1572 or equivalent. Investigational study drug use, other than as directed by this protocol, is not allowed.

All unused vials of Qapzola are to be accounted for at the site and maintained in a secured, locked storage area with access limited to authorized study personnel only. Used Qapzola vials will be destroyed per institution, local, and all applicable policies and procedures. After study conclusion, all unused vials of Qapzola may be destroyed at the site, following verification of accountability by a Sponsor representative.

9.3 Protocol Compliance

The Principal Investigator is responsible for ensuring the study is conducted in accordance with the procedures and evaluations described in this protocol.

9.4 Sponsor Responsibilities

9.4.1 Study Monitoring

The study will be monitored by employees or representatives of Spectrum. CRAs will monitor each site on a periodic basis and perform verification of source documentation for each patient as well as other routine compliance reviews. Spectrum's Medical Monitor and Pharmacovigilance Department will review safety data and be responsible for ensuring timely reporting of expedited SAERs to regulatory agencies and Investigators.

9.4.2 Safety Monitoring

The clinical drug safety of study treatment will be continuously evaluated by the study Medical Monitor or designee on an ongoing basis during the course of this clinical study. All SAEs related to study treatment in this study and all other ongoing clinical studies with study treatment will be processed in compliance with current regulatory guidelines by Spectrum's Pharmacovigilance Department. This processing will include a formal assessment of each SAE by drug safety. An Independent Data Monitoring Committee (IDMC) will review the unblinded safety data from the first 30 patients to verify that the 8 mg/50 mL dose is safe. In addition, a cumulative review of all SAEs from all sources will be assessed periodically.

9.5 Joint Investigator/Sponsor Responsibilities

9.5.1 Access to Information for Monitoring and Auditing

In accordance with ICH GCP guidelines and 21 CFR 312, the CRA/auditor is to have direct access to the patient's source documentation in order to verify the data recorded in the CRFs. The CRA is responsible for routine review of the CRFs at regular intervals throughout the study and to verify adherence to the protocol, as well as the completeness, consistency, and accuracy of the data being recorded. The CRA/auditor is to have access to any patient records needed to verify the entries on the CRFs, as well as access to all other study-related documentation and materials. The Investigator agrees to provide the monitor with sufficient time and facilities to conduct monitoring.

9.5.2 Termination of the Study

For reasonable cause, either the Investigator or Spectrum may terminate the Investigator's participation in this study. In addition, Spectrum Pharmaceuticals Inc. may terminate the study at any time upon immediate notice for any reason, including but not limited to, Spectrum's belief that termination is necessary for the safety of patients.

9.5.3 Publication Policy

To coordinate the dissemination of data from this study, Spectrum encourages the formation of a publication committee consisting of the Principal Investigator and appropriate Spectrum staff. The committee is expected to solicit input and assistance from other Investigators and Sponsor

staff as appropriate. Membership on the committee (both for Investigators and Staff) does not guarantee authorship- the criteria described below should be met for every publication.

Authorship of any publications resulting from this study will be determined on the basis of the Uniform Requirements for Manuscript Submitted to Biomedical Journals (International Committee of Medical Journal Editors, 2005), which states:

- Authorship credit should be based on the following; authors should meet all three conditions:
 - Substantial contributions to conception and design, acquisition of data, or analysis and interpretation of data;
 - Drafting the article or revising it critically for important intellectual content; and
 - Final approval of the version to be published.
- When a large, multicenter group has conducted the work, the group should identify the individuals who accept direct responsibility for the manuscript. These individuals should fully meet the criteria for authorship defined above.
- Acquisition of funding, collection of data, or general supervision of the research group alone does not constitute authorship.
- All persons designated as authors should qualify for authorship, and all those who qualify should be listed.
- Each author should have participated sufficiently in the work to take public responsibility for appropriate portions of the content.

All publications (eg, manuscripts, abstracts, oral/slide presentations, books chapters) based on this study must be submitted to Spectrum within 30 days (but no less than 10 days) prior to submission or publication for corporate review.

9.6 Confidentiality

All information provided to the Investigator by Spectrum, including nonclinical data, protocols, CRFs, and verbal and written information, will be kept strictly confidential and confined to the clinical personnel involved in conducting this study, and no disclosure shall be made except in accordance with any right of publication granted to the Investigator. All personnel will handle patient data in a confidential manner in accordance with applicable regulations governing clinical research. Upon request by a regulatory authority such as the US FDA and other regulatory authorities worldwide, the Investigator/institution is to make available for direct access all requested study-related records or reports generated as a result of a patient's participation in this study. This information may be related in confidence to the IRB/EC or other committee functioning in a similar capacity. In addition, no reports or information about the study or its progress will be provided to anyone not involved in the study other than to Spectrum, or in confidence to the IRB/EC or similar committee, except if required by law.

APPENDIX 1: SCHEDULE OF STUDY ASSESSMENTS AND PROCEDURES

Assessments	Screening	Randomize/ Treatment	Safety Follow-up Visit ^a	Long-Term Post-TURBT Follow-up ^b									
	Day -30 to 1	Day 1	Day 35	Month								Every 6 Months	
				3 ^a	6	9	12	15	18	21	24		
	Visit 0	Visit 1	Visit 2	Visits 3-10								Visits 11+	
Informed Consent (IC)	x												
Urine cytology	x ^c			x	x	x	x	x	x	x	x	x	x
Cystoscopy	x ^c			x	x	x	x	x	x	x	x	x	x
Medical history	x												
Vital signs	x	x	x	x									
Weight and height	x												
Physical examination ^d	x		x	x									
Complete Blood Count	x	x ^e	x	x									
Chemistry	x	x ^e	x	x									
Pregnancy test	x												
Urine dip stick	x	x ^{e,f}	x	x	x	x	x	x	x	x	x	x	x
TURBT and Specimen Collection		x ^g											
Randomization		x											
Qapzola or Placebo instillation ^h		x											
Concomitant medications ⁱ	x	x	x	x	x	x	x	x	x	x	x	x	x
Adverse event assessment ^j	x	x	x	x	x	x	x	x	x	x	x	x	x

- a) Only patients who don't have pathology confirmed study-eligible NMIBC after TURBT, or patients who discontinue during follow-up, will return on Day 35 (±5 days) for the Safety Follow-up Visit. Patients in the Target Population will have the Safety Follow-up at the 3-month visit.
- b) Follow-up visits for patients with Ta histology are to be conducted every 3 months (±30 days) calculated from the date of TURBT for the first 2 years and then every 6 months (±60 days) until tumor recurrence or the End-of-Study, whichever occurs first.
- c) The qualifying cystoscopy and urine cytology may be performed up to 45 days prior to signing the informed consent.
- d) A complete physical examination will be performed at Screening and the Safety Follow-up Visit/Month 3 Follow-up Visit. At all other visits, a physical examination is only required as indicated.
- e) If the screening assessments for the physical examination, hematology, chemistry, urine dipstick were performed within 3 days (72 hours) prior to Day 1/TURBT, these assessments do not need to be repeated at the Day 1 Visit. If patient is on anticoagulation therapy or has bleeding disorder risk, PT/PTT test should be ordered at Screening per investigator discretion.
- f) Urine dipstick to be done just prior to study drug instillation (60 ± 30 minutes) once gross hematuria is resolved.
- g) Each tumor/lesion resected during TURBT should be submitted to the local pathology lab in a separate container, noting the location, to ensure that the tumor location, size, stage, and grade for each tumor/lesion, according to the 2004 WHO/ISUP grading system along with the presence/absence of muscle fiber in the lesion, is assessed.
- h) Instillation of study drug (Qapzola or placebo) is to be performed at 60 ± 30 minutes post-TURBT procedure on Day 1 and is to be retained in the bladder for 60 ± 5 minutes.
- i) During the Follow-up Period, only medications to treat NMIBC will be recorded for concomitant medications.
- j) All adverse events from the time of study drug administration until 35 days after the last dose of study treatment will be recorded. From the 3-month visit through the End-of-Study, only deaths and AEs related to study procedures will be recorded.

Official Title: A Randomized, Multicenter, Two-Arm, Single-Dose, Double- Blind, Placebo-CONTROLLED Phase 3 Study of Intravesical Qapzola™ (Apaziquone) as a Chemotherapy Adjuvant to TransUrEthral Resection of Bladder Tumors in Patients with Low- to Intermediate-Risk Non-Muscle Invasive Bladder Cancer (CONQUER)

NCT Number: NCT03224182

Document Date: SAP Version 1.0: 30 May 2019

STATISTICAL ANALYSIS PLAN

Study: SPI-QAP-306

Title: A Randomized, Multicenter, Two-Arm, Single-Dose, Double-Blind, Placebo-CONTROLLED Phase 3 Study of Intravesical Qapzola™ (Apaziquone) as a Chemotherapy Adjuvant to TransUrEthral Resection of Bladder Tumors in Patients with Low- to Intermediate-Risk Non-Muscle Invasive Bladder Cancer (CONQUER)

Sponsor: Spectrum Pharmaceuticals, Inc.

Version: 1.0

Date: 30 May 2019

Author: [Redacted] 8/27/2020

[Redacted], PhD Date
[Redacted]

Approval: [Redacted] 8/27/2020

[Redacted], PhD Date
[Redacted]

Summary of Changes from protocol

The SAP is to accommodate the early termination of the study due to business reason. Important changes are summarized below.

1. All efficacy objectives are removed.
2. All efficacy endpoints are removed, including all corresponding analysis.
3. The following Analysis Populations are removed.
 - Target Population
 - Non-Target Population
 - Per-Protocol (PP) Population
4. Interim Analysis is removed.
5. Sensitivity analysis and subgroup analysis are removed.

TABLE OF CONTENTS

TABLE OF CONTENTS	3
1 INTRODUCTION	4
2 STUDY OBJECTIVES	4
2.1 Primary Objective.....	4
3 INVESTIGATIONAL PLAN	4
3.1 Study Population.....	4
3.2 Study Design	4
3.3 Study Duration	5
3.4 Study Endpoints.....	5
3.4.1 Efficacy Endpoints.....	5
3.4.2 Safety Endpoints.....	5
4 STATISTICAL CONSIDERATIONS.....	5
4.1 General Analysis Considerations.....	5
4.2 Sample Size	5
4.3 Randomization	6
4.4 Baseline Measurements	6
4.5 Handling of Missing Data.....	6
4.6 Analysis Population	7
4.7 Final Analysis	7
5 STUDY PATIENTS.....	7
5.1 Disposition of Patients	7
5.2 Pretreatment Characteristics.....	7
6 EFFICACY EVALUATION.....	7
7 SAFETY EVALUATION	7
7.1 Extent of Exposure.....	7
7.2 Concomitant Medications	7
7.3 Adverse Events	7
7.3.1 Treatment Emergent Adverse Events.....	7
7.3.2 Treatment-Related Adverse Events	8
7.3.3 Serious Adverse Events	8
7.3.4 Other Important Adverse Events.....	8
7.4 Clinical Laboratory Evaluations	8
8 REFERENCES	8

1 INTRODUCTION

This statistical analysis plan (SAP) includes information on statistical design of this clinical study, definitions of efficacy and safety endpoints, and plans for the analysis of primary and secondary endpoints of the study. The statistical methods and analyses described here are based on those presented in the clinical study protocol, and supersede definitions and procedures described in any other past and/or present documents regarding the statistical analyses of the efficacy and safety endpoints of study **SPI-EOQ-13-306**.

2 STUDY OBJECTIVES

2.1 Primary Objective

- To evaluate the safety in patients with low- to intermediate-risk NMIBC who receive either 8 mg Qapzola or placebo post- TransUrEthral Resection of Bladder Tumors (TURBT).

3 INVESTIGATIONAL PLAN

3.1 Study Population

Patients with low- to intermediate-risk non-muscle invasive bladder cancer, who satisfy all protocol-defined enrollment criteria, are eligible to enroll in this randomized study.

3.2 Study Design

This is a randomized, multicenter, two-arm, double-blind, placebo-controlled study of Qapzola in patients with low- to intermediate-risk NMIBC.

At Screening, patients will undergo an assessment of urothelial carcinoma of the bladder via cystoscopy for clinically apparent tumor of Ta histology, including PUNLMP.

On **Day 1**, eligible patients will be randomized to one of the two treatment arms in a 2:1 ratio:

- **Arm 1- One Dose of 8 mg Qapzola**
- **Arm 2- One Dose of Placebo**

Once randomized, patients will undergo TURBT on **Day 1** and the study drug instillation will occur at 60 ± 30 minutes post-TURBT and will be retained for 60 minutes (± 5 minutes) in the bladder. All histology specimens will be reviewed by a local pathology laboratory and all clinical treatment decisions will be based on the local pathology review. The target study population is low- to intermediate-risk patients who have Ta histology, including PUNLMP, as confirmed by a pathology laboratory. Patients with strongly suspected PUNLMP at Screening or TURBT should not be enrolled in the study. Patients whose tumor histology does not meet the criteria for eligibility, as confirmed by pathology (**Non-Target Population**), will be followed up for safety on **Day 35** (± 5 days) (**Safety Follow-up Visit**) and will then be discontinued from the study. If the pathology results are delayed beyond 35 days, the **Safety Follow-up Visit** will be conducted when the results are available for these patients.

Patients who have pathology confirmed target histology will not receive additional treatment for NMIBC during the follow-up prior to recurrence. All patients will be followed until either a confirmed tumor recurrence or the **End-of-Study**, whichever occurs first.

3.3 Study Duration

The total duration of the study for each patient will be approximately 5 years including:

- **Screening Period:** up to 30-days
- **Treatment: Day 1**
- **Safety Follow-up: Day 35** (± 5 days) (non-**Target Population**) or Month 3 Follow-up Visit (**Target Population**)
- **Follow-up Period:** No follow-up in non-**Target Population**. Until either a confirmed tumor recurrence or the **End-of-Study**, whichever occurs first in the **Target Population**.

The study was terminated early due to business reason and no patient was followed more than 24 months.

3.4 Study Endpoints

3.4.1 Efficacy Endpoints

The study was terminated early due to business reason and analysis for efficacy endpoints will not be performed.

3.4.2 Safety Endpoints

- All TEAEs
- Treatment related adverse events
- Serious Adverse Events (SAEs)
- TEAEs leading to drug discontinuation
- Routine laboratory test parameters (hematology, chemistry)
- Deaths

4 STATISTICAL CONSIDERATIONS

4.1 General Analysis Considerations

The statistical analyses will be reported using summary tables, figures, and data listings. All analyses and tabulations will be performed using SAS[®] Version 9.4 or higher. All tables, listings, and figures will be validated and reviewed before being finalized. Tables will be reviewed for accuracy, consistency with this plan, consistency within tables, and consistency with corresponding output.

For the continuous variables, number of non-missing values and mean, standard deviation, median, minimum, and maximum will be tabulated by treatment arm. For the categorical variables, the counts and percent for each possible value will be tabulated by treatment arm.

4.2 Sample Size

The sample size calculation assumes a hazard ratio (HR) of 0.65 based on the results from previous Phase 3 studies (**SPI-611 and SPI-612**) of Qapzola and placebo comparisons overall and in the drug instillation time window 31-90 minutes post-TURBT. The enrolled patients will be randomized in a 2:1 ratio to either Qapzola or placebo.

Approximately 500 patients will be enrolled and treated in this study. Accrual time is estimated as 24 months and follow-up time as approximately 24 months. For the sample size calculation, a hazard ratio (HR) of 0.65 is assumed for the improvement in **Time to Recurrence** in favor of Qapzola as compared to the placebo with a hazard rate of 0.3 in placebo arm. In a 2:1 randomization of Qapzola and placebo, sample sizes of 284 in APZ and 141 in PBO Target disease patients (total of 425) will provide 85% power. This sample size is estimated to provide a total of 208 recurrence events during the follow-up duration of at least 24 months.

The study was terminated early due to business reason and patient recruitment was incomplete.

4.3 Randomization

The randomization plan will use a permuted block design and will not be stratified. Study drug kits will contain either vials of Qapzola or placebo. Patients will be randomized within a center. Patient numbers will be assigned sequentially at each site.

Patients who meet all eligibility criteria may be considered for randomization. Eligibility of all patients will be reviewed and approved for randomization by the Sponsor's Medical Monitor, or designee. Patients approved for randomization will be randomized 2:1 to receive either one instillation of 8 mg Qapzola (**Day 1**) or one dose of placebo.

4.4 Baseline Measurements

Baseline measurement of any variable for each patient will be the last available value of the variable on or before the date of **Visit 1, Day 1**, which is the day on which the patient undergoes TURBT and first study drug instillation.

4.5 Handling of Missing Data

Except for partial dates, missing data will not be imputed. That is, the analyses will be performed considering all observed data.

For the date of historical events prior to the study, if the month and day are missing, the date will be imputed as July 1. If the day is missing, it would be imputed as the 15th of the month.

For start date of adverse events and concomitant medications, if the month is missing and the year is the same as the year of randomization, it is assumed that the event is treatment-emergent, and that the medication is taken during the study, unless the stop date occurs prior to the first dose date. In such cases, the start date is imputed as the date of first dose of study drug.

If the year is missing, no imputation will be done for the year, and the entire date variable will be set to missing, and the AE is assumed to be treatment emergent, and concomitant medication is assumed to be started during the study.

The imputed date value will only be used for the calculation of derived variables. The originally collected date value will be presented in the data listings.

For the dates of events which occurred during the study, a missing day is set to the 15th of the month. No imputation will be performed if month or year is missing, however missing values will be queried.

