7.3 Adverse Events

An overall summary table of treatment emergent adverse events (TEAE) will be provided. The summary will include any TEAE, TEAE by severity, SAE, TEAE and SAE leading to study drug discontinuation, any treatment-related AE, treatment-related AE by severity, treatment-related SAE, and treatment-related AE leading to study drug discontinuation.

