7.3.1 Treatment Emergent Adverse Events

A TEAE is any AE that occurs from the first dose of study treatment until 35 days after the last dose of study drug administration. TEAEs will be graded according to National Cancer Institute

Common Terminology Criteria for Adverse Events (NCI CTCAE) version 4.03, and grouped by the MedDRA preferred term, and summarized by worst grade severity per patient by treatment arms.

The incidences of treatment emergent AEs will be presented by MedDRA SOC and PT with any grade and with Grade 3 or 4. Patients who experience more than one type of AE will be counted under each of the corresponding PT. Patients who experience different episodes of the same AE will be counted only once under the corresponding PT. Similarly, for determination of MedDRA SOC incidences, patients who experience multiple AEs under the same SOC will be counted only once for that SOC. Listing of all TEAEs will also be provided.

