7.3.2 Treatment-Related Adverse Events

Assessment of relatedness to study drug for all AEs will be classified by investigators and reported. “Definitely related”, “probably related” and “possibly related” AEs will be considered as treatment related. An AE will be assigned as treatment-related if the relationship to study drug is missing.

The incidences of treatment-related AEs will be presented by MedDRA SOC and PT with any grade and with Grade 3 or 4.

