7.3.3 Serious Adverse Events

Serious adverse events are those events that result in death, are life-threatening, require or prolong inpatient hospitalization, result in persistent or significant disability/incapacity, or cause congenital anomaly/birth defect.

All SAEs will be provided in listing and the incidence will be summarized in the overall summary of TEAE table.

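### The SAP's missing-day rule has no floor at the dosing date, so an AE dated only to the dosing month is placed before dosing when instillation was on the 16th or later

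*SAP*

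**What the plan says.** SAP 4.5 treats partial AE start dates in two places.

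- **AE-specific rules.** If the month is missing and the year is the year of randomization, the AE is taken as treatment-emergent and its start is set to the first dose date, unless the stop date is before dosing. If the year is missing, the whole date is left missing and the AE is again taken as treatment-emergent.
- **General rule for on-study dates.** "For the dates of events which occurred during the study, a missing day is set to the 15th of the month". The next sentence reads: "No imputation will be performed if month or year is missing, however missing values will be queried".

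No AE-specific rule covers a known month and year with a missing day. On how imputed dates are used, the section says: "The imputed date value will only be used for the calculation of derived variables".

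SAP 7.3.1 defines a TEAE as "any AE that occurs from the first dose of study treatment until 35 days after the last dose". There is a single dose, given on Day 1. The flag drives several outputs. SAP 7.3 says: "An overall summary table of treatment emergent adverse events (TEAE) will be provided". SAP 7.3.1 adds the incidence tables and states: "Listing of all TEAEs will also be provided".

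Protocol 5.4.10 restricts recording before dosing to SAEs related to study procedures. From dosing, all AEs are recorded until Day 35 (non-Target patients) or Month 3 (Target patients).

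**The concern.** The rules run in the wrong order. An AE about which less is known (month or year missing) stays treatment-emergent, while an AE about which more is known (month given, day missing) can be moved before the dose. Given the protocol's recording rules, a non-serious AE dated to the dosing month should hardly ever be pre-dose, so the imputed date contradicts what the data collection already tells us.

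Events moved in this way drop out of the overall TEAE summary, the TEAE incidence tables and the TEAE listing. SAP 4.7 leaves safety as the only analysis in this terminated study, so these are its main outputs.

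Missing days are plausible. The schedule of assessments gives Target patients no scheduled visit between Day 1 and Month 3, so an AE that starts shortly after discharge may be reported from memory weeks later.

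Two smaller gaps sit in the same section. The SAP does not say that the AE missing-month rule overrides the general statement that nothing is imputed when the month is missing. Nor does it give the treatment-emergent status of an AE with a missing month in the calendar year after dosing.

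**Working it through.** There is no plan figure to reproduce, so the check applies the rule as written.

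**Inputs from the documents.** Missing day set to the 15th (SAP 4.5); TEAE window from dosing to 35 days after it (SAP 7.3.1); one dose, on the day of TURBT (SAP 4.4).

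**Assumptions.** Dosing dates are spread evenly over the calendar. The documents do not give the timing of AE onset, so a range is shown. Below, *k* is the number of days from instillation to true onset, with the instillation day as 0.

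**Step 1: the threshold.** For an AE dated to the dosing month, imputed onset minus dosing date is 15 − D, where D is the day of the month of instillation. D = 14 gives +1, D = 15 gives 0, D = 16 gives −1, D = 20 gives −5 and D = 30 gives −15. The AE becomes pre-dose exactly when D is 16 or more.

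**Step 2: how often this happens.** An onset at day *k* is moved before dosing when D ≥ 16 and the onset is still in the dosing month, that is 16 ≤ D ≤ L − k for a month of L days. That is max(0, L − 15 − k) dosing dates per month. A four-year cycle has 1,461 dates in 48 months: 28 of 31 days, 16 of 30, one of 29 and three of 28. For k ≤ 13 the count is 1,461 − 48×15 − 48k = 741 − 48k. For k = 14 it is 28×2 + 16×1 = 72, for k = 15 it is 28, and from k = 16 it is 0.

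| True onset | Dates moved | Share of 1,461 |
|---|---|---|
| day 0 | 741 | 50.7% |
| day 1 | 693 | 47.4% |
| day 3 | 597 | 40.9% |
| day 7 | 405 | 27.7% |
| day 10 | 261 | 17.9% |
| day 13 | 117 | 8.0% |
| day 14 | 72 | 4.9% |
| day 15 | 28 | 1.9% |
| day 16 or later | 0 | 0% |

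**Step 3: averages over onset windows.**

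- Days 1-13: (13×741 − 48×91) / (13×1,461) = 5,265 / 18,993 = 27.7%.
- Days 0-35: (741 + 5,265 + 72 + 28) / (36×1,461) = 6,106 / 52,596 = 11.6%.
- Days 14-35: (72 + 28) / (22×1,461) = 100 / 32,142 = 0.3%.

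**Step 4: alternatives.** Enumerating every dosing date against every onset day gives:

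| Rule | Moved before dosing (onset days 0-35) | Onsets on days 36-90 called TEAE |
|---|---|---|
| SAP: the 15th | 11.6% | 7.6% |
| 15th, floored at instillation in the dosing month | 0% | 7.6% |
| Instillation date in the dosing month, 1st in later months | 0% | 26.8% |

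The 15th also pushes 9.6% of onsets uniform over days 0-35 past Day 35. The floor leaves that figure unchanged.

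**The case against.** **The general rule may not govern AE start dates.** Those dates have their own paragraphs, and reading the last paragraph as covering them sets its missing-month sentence against the AE missing-month rule. On the narrower reading, the SAP has no missing-day rule for AE starts, and a programmer would probably follow the treatment-emergent default. That is a fair reading, but it does not remove the problem: these AEs then have no stated rule and still no floor.

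**The effect may be very small.** Recruitment was incomplete, AEs are asked about at every visit, and CRFs are checked against source. If, as an assumption, 1-5% of TEAEs lacked a day, then with onsets uniform over days 0-35 the loss would be 0.01×11.6% to 0.05×11.6%, or about 0.1-0.6% of TEAEs. The largest percentages belong to dosing-day onsets, which are the least likely to lack a day because AEs are assessed on Day 1. The recall argument is weaker for non-Target patients, who are seen at Day 35. All of this stands and limits the weight of the point.

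**Little depends on the flag.** No between-arm test is planned, and the error follows the calendar, so it does not favor an arm by design. The serious events remain visible: "All SAEs will be provided in listing". The treatment-related table is, on its wording, not confined to TEAEs: "Assessment of relatedness to study drug for all AEs will be classified by investigators and reported". These points also stand.

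**The floor is a partial cure.** With onsets uniform over days 0-35, 9.6 / (11.6 + 9.6) = 45% of the lost TEAEs stay lost, at the Day 35 end. Calling every AE treatment-emergent unless its partial date rules that out would recover them. In later months, however, that classifies events just as imputing the 1st does. It would therefore call 26.8% of missing-day onsets on days 36-90 TEAEs, against 7.6%, in Target patients whose AEs are recorded to Month 3. The floor has no such cost.

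**Conclusion.** The concern holds. Followed as written, SAP 4.5 dates an AE known only to the dosing month before the dose for every instillation on the 16th or later (50.7% of dates), and the event loses its TEAE status. Depending on onset, the share of missing-day TEAEs lost is 50.7% on the dosing day, 27.7% over days 1-13, 11.6% over days 0-35 and nil from day 16. These figures rest on evenly spread dosing dates and assumed onset timing.

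The absolute effect cannot be stated, because the number of missing-day AEs is not given and may be zero. The expected consequence is some undercounting of TEAEs in both arms, not a biased comparison. It should be corrected: the stated rule gives a wrong result, and the TEAE tables are the core of what remains. The two smaller gaps in SAP 4.5 are missing detail only; the conclusion does not depend on them.

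**What to change.** In SAP 4.5, add for AE start dates with a missing day: use the 15th, but if month and year equal those of instillation, use the later of the 15th and the instillation date, unless the stop date is before dosing. Do not switch to the 1st of the month for later months.

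In the same edit, state that the AE missing-month rule takes precedence over the general sentence against imputing, and give the treatment-emergent status of an AE with a missing month in the year after dosing.

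The cost is two or three sentences and one programming condition. TEAE counts may rise slightly. A procedure-related SAE that truly occurred before dosing, with a missing day in the dosing month, would count as a TEAE unless its stop date shows otherwise.
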